1.3. Treatment Assignment and Blinding

The dosing regimen and schedule for this study are as follows:

- TD-1473 20 mg (2 x 10 mg tablets) once daily: Taken orally for up to 3 years in the morning. With the exception of clinic visit days, subjects will be instructed to take two tablets once daily at approximately the same time each morning.
- TD-1473 80 mg (2 x 40 mg tablets) once daily: Taken orally for up to 3 years in the morning. With the exception of clinic visit days, subjects will be instructed to take two tablets once daily at approximately the same time each morning.
- TD-1473 200 mg (2 x 100 mg tablets) once daily: Taken orally for up to 3 years in the morning. With the exception of clinic visit days, subjects will be instructed to take two tablets once daily at approximately the same time each morning.

Maintenance of the Blind

In order to maintain the blind in subjects whose treatment is known once database lock has occurred for the Maintenance Study, a firewall will be maintained ensuring that Sponsor employees who are aware of treatment assignments will not have contact with site personnel.

In order to maintain the study blind, the study medications will have a label containing the study name, Kit ID number, and reference number. The KIT ID number will be automatically entered in the case report form (CRF) when the drug is dispensed. The study medications will be identical in appearance and packaging.

The investigator will not be provided with randomization codes. The codes will be maintained within the Randomization and Trial Supply Management System (RTSM), which has the functionality to allow the investigator to break the blind for an individual subject. The date and reason for the unblinding will be documented in the appropriate section of the CRF and in the source document. The documentation received from the RTSM indicating the code break will be retained with the subject's source documents in a secure manner. Subjects who had their treatment assignment unblinded by the investigator will be discontinued from study medications.

Data that may potentially unblind the treatment assignment (i.e., study medication, plasma concentrations and treatment allocation) will be handled by the use of subject aliases at the Bioanalytical Lab that conducts initial data analyses to ensure that the integrity of the blind is maintained and the potential for bias is minimized when transferring said information to the Sponsor.

██
██

Treatment assignment blinding will be maintained for investigative sites, site monitors, and subjects participating in this protocol until the analyses for the study have been completed.

An independent DMC will regularly review unblinded safety data. The committee and its statistical support group will have access to unblinded treatment information. They will not divulge any information to the Sponsor that may potentially unblind an individual subject's treatment group.

1.4. Schedule of Assessments

Table 4: Schedule of Study Procedures

Study Procedures	Day 1	WEEK VISITS +/- 5 Days								Early Study Drug Discontinuation ^l + 5 days from last dose	EOS 4 Weeks Post Last Dose ^l - 3 to + 5 days
		Year 1	W4	W12		W24	W36	W48	W52		
		Year 2			W60	W72	W84	W96	W104		
		Year 3			W108	W120	W132	W144	W156		
Informed Consent	X										
Review Inclusion/Exclusion Criteria	X										
Physician Global Assessment (PGA)	X		X	X	X	X	X	X	X	X	X
Pregnancy Test (females of child-bearing potential)	X		X ^e	X ^e	X ^e	X ^e	X ^e	X ^e	X ^e	X ^e	X ^e
FSH	X ^a										
████████████████████	■			■		■		■		■	■
In Clinic Dosing - Study Drug Dosing	X ^k										
Vital Signs (Temp, HR, BP, Respirations)	X ^l		X ^l	X ^l	X ^l	X ^l	X ^l	X ^l	X ^l	X	X
Safety Laboratory (Chemistry, Hematology)	X ^{a, m}		X	X	X	X	X	X		X	X
Physical Exam	X ^a		X	X	X	X	X	X	X	X	X
Smoking Status	X ^a								X		X
Weight	X ^a								X		
Medical History / Demographics	X ^{a, b}										
Concomitant Medication /Adverse Event Review	X		X	X	X	X	X	X	X	X	X
Overnight Fasting Lipid Panel			X	X	X	X	X	X		X	X
████████████████████	■		■	■	■	■	■	■	■	■	■
████████████████████									■		
████████████████████									■		
12-Lead Electrocardiogram (ECG)	X ^a			X				X	X		
Study Drug Dispensing	X		X	X	X	X	X	X	X ^e		
Study Drug Accountability			X	X	X	X	X	X	X	X	
Subject eDiary Daily Compliance Review			X ^h	X ^h							
Subject Symptom Recall and Compliance Review					X ⁱ	X ⁱ	X ⁱ	X ⁱ	X ⁱ	X ⁱ	
Dispense Subject eDiary	X ^h										
Return of Subject eDiary				X ^a							

Non-Site Study Procedures (Calculations for Programming/Statisticians and applicable suppliers)											
			■	■	■	■	■	■	■	■	■
									■		

- a. Subject will be enrolled into the Protocol 0164 (LTS) and undergo treatment-assignment on Day 1 after subject has signed informed consent and is confirmed to be eligible for the study. **Note:** the first visit of Protocol 0164 (LTS) is Day 1 and will include Study Drug intake. Subjects exiting Protocol 0157 who have already taken Study drug from Protocol 0157 will need to return to the Clinic on another day prior to consenting to LTS in order to ensure that they are able to take LTS Day 1 Study Drug in clinic. Subjects **should not** receive Protocol 0157 Study Drug AND Protocol 0164 (LTS) Study Drug on the same day. Day 1 of Protocol 0164 (LTS) should be within 14 days of subject exiting the Maintenance Study. If any listed study procedure has been completed in the last 14 days in the Protocol 0157 prior to Day 1, it does not need to be repeated during Protocol 0164 (LTS) Day 1.
- b. Medical history information, AE's and partial Demographic data will be collected from the Protocol 0157 database, if applicable. Additional demographic data may be required to be entered into the Protocol 0164 (LTS) database.
- [REDACTED]
- [REDACTED]
- e. Urine b-hCG testing will be done before every visit for women of childbearing potential to confirm absence of pregnancy before dispensation of study drug. If the urine b-hCG test is positive, a serum b-hCG test must be performed.
- [REDACTED]
- g. Study drug will be dispensed for subjects to administer daily at home **with the exception** of Week 156 which is the last treatment visit.
- h. Subjects will continue to complete the electronic diary **on a daily basis for the initial 12 weeks** of the LTS. Subjects will be instructed on daily diary completion, including symptom monitoring (rectal bleeding and stool frequency) as well as study drug dosing details from Day 1 through to Week 12. Subjects will be counseled on missed diary entries and missed study drug doses. Subjects will return the electronic diaries at Week 12.
- i. After Week 12 subjects will be contacted approximately 10 days ±2 days preceding each clinic visit to be reminded that they will be asked to recall their symptoms (rectal bleeding, bowel movements and study drug dosing) for the 7 days prior to clinic visit.
- j. Early Discontinuation is for subjects who prematurely discontinue the study drug. This visit will be conducted within 5 days after the last dose of study drug. Subjects will also return for the EOS visit for collection of safety data and assessment of disease activity.
- k. Subjects **should not** receive Protocol 0157 Study Drug AND Protocol 0164 Study Drug on the same day.
- l. Obtain blood pressure and heart rate anytime pre-dose at all visits.
- m. If safety laboratory testing is required at Day 1, results from Safety Laboratory Test from Day 1 are not required to be received before enrolling the Subject into Protocol 0164 and dispensing Study Drug.
- n. Required for any female that may have become or is suspected to be postmenopausal since enrolment in Protocol 0157

1.5. Sample Size Determination

The sample size will depend on the number of subjects who are eligible and elect to enter from the Maintenance Study of Protocol 0157. Prior to study termination it was anticipated that approximately 500 subjects will receive TD-1473 for up to 156 weeks (3 years).

2. ANALYSIS SETS

The Safety analysis set, comprising all subjects receiving at least one LTS dose of TD-1473, will be the analysis set for all summaries except some enrollment summaries.

3. STATISTICAL ANALYSES

3.1. General Considerations

All individual data will be listed as measured. All statistical summaries and analyses will be performed using SAS software (SAS Institute, Cary, North Carolina, USA).

All data from scheduled and unscheduled visits will be presented in the subject listings. However, unless noted otherwise, only data from scheduled/windowed visits will be included in the summaries, statistical analysis, and calculation of derived parameters.

Summary tables and listings (e.g., post text tables and individual subject data listings are prepared according to ICH Guideline E3) include a “footer” providing explanatory notes.

Continuous data will be summarized using an 8-point descriptive summary (n, mean, standard deviation, median, interquartile range [25% quartile, 75% quartile]), minimum, and maximum) unless otherwise specified.

Categorical data will be summarized using counts and percentages. Percentages will be shown to 1 decimal place and percentages for zero counts will be omitted.

For safety assessments, summary statistics will be reported by treatment.

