1.2. Study Design

This LTS Study 0164 will utilize a multi-center, parallel-group design to evaluate the safety of long-term TD-1473 treatment in subjects with moderate to severe UC rolling over from Protocol 0157 for up to 3 years.

Subjects eligible for the study are those who are rolling over from Protocol 0157 Maintenance Study who meet all inclusion and no exclusion criteria, including having achieved clinical response during an Induction Study and during the Maintenance Study who:

- a) demonstrate persistent [REDACTED] loss of response (no improvement for approximately 6 to 8 weeks after meeting loss of response criteria despite more time on study drug and potentially concurrent rescue medication)

OR

- b) have repeated (two) Clinical Flares after an episode [REDACTED]
[REDACTED]

OR

- c) complete the Maintenance Study and confirmation of clinical remission status results are available [REDACTED]
[REDACTED]

All subjects will receive active drug at three dose levels of 20 mg, 80 mg and 200 mg, and thus, this study will not be placebo-controlled, but blinding as to the specific dose of TD-1473 will be maintained. The dosing regimen for subjects ([Table 3](#)) entering the Long-Term Study from the Maintenance Study will be based on:

1. The subject's clinical remission status from Protocol 0157 upon entry into the LTS Study
2. The subject's study drug assignment during the Protocol 0157 Maintenance Study.

[figure not shown]
Subjects entering the LTS Study after completing the Maintenance Study in clinical remission on active drug will continue with the same dose of TD-1473. Subjects entering the LTS Study after completing the Maintenance Study in clinical remission on placebo will be placed on 20 mg.

Subjects who enter the LTS Study not in clinical remission on TD-1473 upon completion of the Maintenance Study and subjects who exit the Maintenance study prematurely due to persistent loss of response or recurrent clinical flare with loss of response (also not in clinical remission) will receive an escalated dose in the LTS Study, based on their Maintenance Dose. Subjects on 20 mg and 80 mg of TD-1473 will be dose-escalated one level up to 80 mg and 200 mg, respectively. Subjects on the highest dose (200 mg) will remain on the highest dose. Placebo subjects entering the LTS Study not in remission will be dose escalated to 80 mg.

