The dose assigned to subjects entering the LTS is thus partially dependent on the clinical remission status upon entry. For subjects completing the Maintenance Study in remission on active drug, continuing on the same dosing regimen will potentially allow for maintenance of clinical benefit and continued assessments for maintenance of response/remission. For subjects on TD-1473 entering LTS with persistent loss of response or recurrent clinical flare after loss of response, dose escalation in LTS may allow for the possibility of achieving clinical benefit and even recapture of clinical response at a potentially higher dose than that administered during the Maintenance Study. For placebo subjects entering LTS not in clinical remission, dose escalation to 80 mg would potentially allow for achievement of clinical response or remission. For placebo subjects entering LTS in clinical remission, escalation to 20 mg would potentially allow for a higher likelihood of maintenance of clinical remission.

After the global, last subject study visit (including the 4 week follow up visit), an analysis of safety data will be performed.

No interim analyses are planned for this study.

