3.1.5. Actual Treatment

Data will be summarized by actual treatment group which will be determined by the treatment that was dispensed at the Day 1 visit.

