3.4.2. Adverse Events

Adverse events (AEs) will be coded to the preferred terms (PT) of the Medical Dictionary for Regulatory Activities (MedDRA®). Summaries will be presented by system organ class (SOC), preferred term, and severity and/or relatedness, the number and percentage of subjects for whom events were reported.

Adverse events (AEs) are recorded from signing of the informed consent form through the final follow-up assessment. Adverse events observed prior to first dose are non-treatment emergent.

Treatment emergent adverse events are defined as follows:

- TEAEs are AEs with onset on or after the first initiation of study drug up to the date of last dose of study drug + 28 days.

Only treatment-emergent AEs will be summarized in the tables. A listing of all TEAEs by subject will be provided.

An AE will be considered a treatment emergent serious AE (TESAE) if it is a TEAE that additionally meets any SAE criteria.

If more than 1 AE is coded to the same preferred term for the same subject, the subject will be counted only once for that preferred term using the most severe and most related occurrence for the summarizations by severity and by relationship to study drug.

Summary tables will also be provided for subjects with:

- TESAEs by SOC and PT
- TEAEs leading to discontinuation of study drug by SOC and PT
- TEAEs leading to temporary interruption of study drug by SOC and PT

- TEAEs by severity and by SOC and PT
- Drug related TEAEs by severity and by SOC and PT

Listings of all AEs, SAEs, AEs resulting in death, and AEs leading to discontinuation by subject will be presented.

An overall summary of adverse events will also be presented and will include the following summary lines: Any AE, Moderate or Severe AEs, AEs Related to Study Drug, Moderate or Severe AEs Related to Study Drug, Serious AEs, Serious AEs Related to Study Drug, AEs Leading to Premature Study Drug Discontinuation, AEs Leading to Temporary Interruption of Study Drug, and Deaths During Study.

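### Crude adverse event percentages by LTS dose mix dose with entry remission status and possibly exposure, and three protocol-planned summaries are absent from the SAP text without being declared

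*SAP*

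**What the plan says.** SAP 3.1: "For safety assessments, summary statistics will be reported by treatment". SAP 3.1.5 defines the groups: "Data will be summarized by actual treatment group which will be determined by the treatment that was dispensed at the Day 1 visit". SAP 3.4.2 sets the statistic for adverse events: "the number and percentage of subjects for whom events were reported".

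SAP 1.2 gives the rule that decides the dose. Subjects completing Maintenance in remission on active drug keep their dose. For the others:
- "Subjects entering the LTS Study after completing the Maintenance Study in clinical remission on placebo will be placed on 20 mg".
- Subjects not in remission move up: "Subjects on 20 mg and 80 mg of TD-1473 will be dose-escalated one level up to 80 mg and 200 mg, respectively". Those already on 200 mg stay there.
- "Placebo subjects entering the LTS Study not in remission will be dose escalated to 80 mg".
- The groups not in remission include "subjects who exit the Maintenance study prematurely due to persistent loss of response or recurrent clinical flare with loss of response".

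The SAP acknowledges the dependence as design background: "The dose assigned to subjects entering the LTS is thus partially dependent on the clinical remission status upon entry".

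SAP 1 records that the study stopped early, with every last dose taken by 09SEP2021, that no inferential tests will be done, and that table specifications are held in a separate document. SAP 3.2.3 lists demographics and body size as the baseline summary. SAP 3.4.1 summarizes exposure on its own.

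**The concern.** TEAE incidence and severity is part of the primary endpoint (Protocol Synopsis, Study Endpoints), and the SAP presents it side by side by dose. The dose groups differ by construction in disease status at entry, and may also differ in how long subjects were observed. A crude difference between 20 mg and the higher doses, or a lack of one, could then reflect who was put on each dose or how long they were followed. The SAP text plans nothing that would let a reader of the synoptic report separate these.

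The second part is a matter of record. Protocol 8.1 says that departures from its planned analyses will be described in the SAP. Two of the summaries missing from the SAP text, TEAEs by exposure duration and the AESI time-to-event plots, are the ones that would have related events to time.

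**Working it through.** There is no power calculation or stated figure to reproduce: the study is descriptive, and the roughly 500 subjects were a roll-over expectation. The check has three steps.

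**1. Composition of the dose groups.** Applying SAP 1.2 to each combination of Maintenance treatment and entry status gives the LTS dose:

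| Maintenance treatment | In remission | Not in remission |
|---|---|---|
| Placebo | 20 mg | 80 mg |
| 20 mg | 20 mg | 80 mg |
| 80 mg | 80 mg | 200 mg |
| 200 mg | 200 mg | 200 mg |

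So 20 mg is fed by 2 cells, of which 0 are non-remitters. 80 mg is fed by 3 cells, 2 of them non-remitters, and 200 mg likewise by 3, of which 2 (2 + 3 + 3 = 8 cells). These are counts of cells, not shares of subjects; the documents give no numbers per cell. Protocol 3.3.2 and SAP 3.6 say that all subjects entering without remission receive an escalated dose, while SAP 1.2 leaves 200 mg subjects where they are. Those passages must be reconciled, but the content of the 20 mg group is the same either way.

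**2. What a crude percentage then measures.** Let p_R and p_N be the TEAE risks of remitters and non-remitters, and s the non-remitter share at a given dose. Suppose there is no dose effect, equal time at risk, and no influence of prior treatment. Then:

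- crude risk at that dose = p_R(1 − s) + p_N·s
- at 20 mg, s = 0, so crude risk = p_R
- gap to 20 mg = s(p_N − p_R)

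The gap is zero only if s = 0 or the two risks are equal, and its sign follows p_N − p_R. If a dose effect exists, this term adds to it or offsets it. None of s, p_N or p_R is in the documents, so no value can be put in.

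Time at risk is a further source of difference. Treatment was planned for up to 156 weeks, but with a common latest last-dose date the longest possible treatment is 09SEP2021 − first LTS dose date + 1 day, which depends on when the subject entered. The SAP text has no rate, no exposure category and no time-to-event display for adverse events. Its treatment duration (3.4.1) ends at the last dose, whereas its TEAE window (3.4.2) runs 28 days longer, so that duration is not a matching denominator.

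**3. Protocol plan against SAP text.**

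| Protocol plan | SAP text | Change described? |
|---|---|---|
| TEAEs by exposure-duration category, categories left to the SAP (8.6.1) | Absent from 3.4.2 | No |
| AESI time-to-event plot for each category with at least one event, timed from first TD-1473 dose (8.6.1.1) | Absent from 3.4.2.1 | No |
| Baseline UC characteristics (8.4.1) | Absent from 3.2.3 | No |
| Enrollment counts by prior treatment and clinical status (8.4.2) | 3.2.1 marked not applicable | Yes, in place |
| Safety subgroups by sex, age, region, steroid use (8.3.2) | 3.5.2 marked not applicable | Yes, in place |
| Efficacy analyses | Excluded | Yes, in SAP 1 and Appendix 1 |

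The first three rows are the undeclared omissions. No claim is made on UC medications, because SAP 3.2.6 is partly redacted.

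**The case against.** The strongest reply is that nothing here departs from the design. The protocol itself plans safety by arm (8.6.1, 8.6.1.1, 8.6.3), the objective is descriptive, no tests are run, and SAP 1.2 openly says that dose depends on remission status. All of that stands, and it rules out the reading that reporting by dose is a mistake.

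A reader might also infer that the report will carry no warning about comparing doses. That cannot be shown. SAP 3.1 provides for explanatory table footers, and the table specifications are in a document not supplied. The point is confined to the SAP text.

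A reader might think that the SAP dropped a promised safety table by entry status. It did not. The protocol's table by those factors was an enrollment count, its safety subgroups do not include remission status, and both removals are marked where they occur.

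It is tempting to say that early exits from Maintenance were followed longer. For the same Maintenance start and a common stop date they could have been, but discontinuation for lack of clinical benefit (Protocol 6.6.1) could shorten their follow-up. Read with SAP 3.1, exposure should at least be visible by dose. What remains is that the text does not link exposure to events.

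Finally, the time-to-event plots are conditional on at least one event in a category, so some might never have been due. That does not remove the need to say that they are no longer planned.

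**Conclusion.** The point holds in limited form. By rule, the non-remitter share is 0% at 20 mg and above 0% at 80 or 200 mg as soon as any non-remitter is assigned there. The crude percentages therefore mix dose with entry status and possibly with exposure. Whether this distorts the picture depends on whether TEAE risk differs by entry status and whether follow-up differs by dose. The documents give neither, so no size or direction is claimed, and it would be wrong to infer that the higher doses will look worse, or better, than they are.

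The finding on undeclared omissions needs no such assumption. Three protocol-planned summaries are absent from the SAP text, and the changes declared in SAP 1 and Appendix 1 concern efficacy only. It assumes only that the redacted parts of the SAP do not contain them.

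The change should be made, because it is cheap and concerns the primary endpoint.

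**What to change.** 1. In SAP 3.2.3, add entry remission status, prior Maintenance treatment and baseline UC characteristics, by dose and overall.
2. In SAP 3.4.2 and 3.4.2.1, repeat the AE overview and the AESI table by entry remission status within dose. The 20 mg non-remitter cell is empty by rule, so only remitters can be set side by side at all three doses, and at 20 mg these include former placebo subjects. Use the footers foreseen in SAP 3.1 to state that the dose groups are not randomized comparisons.
3. Add exposure-adjusted incidence rates (subjects with an event per 100 patient-years) for any TEAE, TESAE and each AESI category, by dose and overall. Count person-time from first LTS dose to the earliest of first event, last dose + 28 days, or last contact, so that it matches the TEAE window.
4. Restore TEAEs by exposure duration and the AESI time-to-event plots, or declare each dropped, with the reason. Do the same for UC characteristics if item 1 is not adopted. Put this in the SAP body, because SAP 1 says that the appendices are not a formal part of the signed plan. If the plots are kept, label their time origin: it is the first TD-1473 dose, not the first LTS dose used for the rates.

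The cost is SAP wording and a few extra tables. Remission status and prior treatment determine the dose, and the dose and last-contact dates are already to be listed under SAP 3.2.2. The UC characteristics are assumed to be available from Protocol 0157. Some cells will be small. Neither the split nor the rates make the dose groups comparable, and the rates address time at risk only. Items 2 and 3 add to the protocol plan; item 4 meets what Protocol 8.1 already asks for.
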